To evaluate the other efficacy of guselkumab in participants with SSc	•	Time to disease worsening: Increase from baseline ≥5 and ≥20% in mRSS OR decrease >10% from baseline in percent predicted FVC
	•	The proportion of participants who experience FVC decline compared with baseline at Week 24 and Week 52
	•	The proportion of participants who experience worsening of FVC at Week 24 and Week 52
	•	Change from baseline in fibrotic change assessed with high-resolution computed tomography (HRCT) at Week 24 and Week 52 in participants with baseline fibrosis/fibrotic changes
	•	The proportion of participants who experience worsening of fibrotic change assessed with HRCT at Week 24 and Week 52
	•	Change from baseline in Frequency Scale for the Symptoms of Gastroesophageal reflux disease (FSSG) score at Week 24 and Week 52
	•	Assessment of nailfold capillaries at Week 24 and Week 52
	•	Change from baseline in Patient global assessment (PGA) at Week 24 and Week 52
	•	Change from baseline in Physician global assessment (PhGA) at Week 24 and Week 52
To evaluate the long-term efficacy of guselkumab in participant with SSc	•	Change from baseline and Week 52 in mRSS at Week 76 and Week 104
	•	The proportion of participants who experience worsening of mRSS at Week 76 and Week 104
	•	The proportion of participants achieving a score of 0.6 in American College of Rheumatology Combined Response Index in dcSSc (ACR CRISS) at Week 76 and Week 104
	•	Change from baseline in forced vital capacity (FVC) and percent predicted FVC at Week 76 and Week 104
	•	The proportion of participants who experience worsening of FVC at Week 76 and Week 104
	•	Change from baseline in the measured absolute diffusing capacity of the lung for carbon monoxide (DLCO) and the derived percent predicted DLCO at Week 76 and Week 104

Objectives	Endpoints
	Change from baseline in Health Assessment Questionnaire-Disability Index (HAQ-DI) score at Week 76 and Week 104
	• Change from baseline in digital ulcer counts at Week 76 and Week 104
	Change from baseline in fibrotic change assessed with high-resolution computed tomography (HRCT) at Week 76 and Week 104 in participants with baseline fibrosis/fibrotic changes
	The proportion of participants who experience worsening of fibrotic change assessed with HRCT at Week 76 and Week 104
	Change from baseline in Frequency Scale for the Symptoms of Gastroesophageal reflux disease (FSSG) score at Week 76 and Week 104

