3. OBJECTIVES AND ENDPOINTS

	Objectives		Endpoints
Pri	mary		
•	To evaluate the efficacy of guselkumab in participants with systemic sclerosis (SSc)	•	Change from baseline in Modified Rodnan Skin Score (mRSS) at Week 24
Sec	ondary		
•	To evaluate the additional efficacy of guselkumab in participants with SSc	•	Change from baseline in mRSS at Week 52
		•	The proportion of participants who experience worsening of mRSS at Week 24 and Week 52
		•	The proportion of participants achieving a score of 0.6 in American College of Rheumatology Combined Response Index in dcSSc (ACR CRISS) at Week 24 and Week 52
		•	Change from baseline in forced vital capacity (FVC) and percent predicted FVC at Week 24 and Week 52
		•	Change from baseline in the measured absolute diffusing capacity of the lung for carbon monoxide (DLCO) and the derived percent predicted DLCO at Week 24 and Week 52
		•	Change from baseline in digital ulcer counts at Week 24 and Week 52
		•	Change from baseline in Health Assessment Questionnaire-Disability Index (HAQ-DI) score at Week 24 and Week 52
•	To evaluate the safety and tolerability of guselkumab in participants with SSc	•	Number and proportion of participants with treatment-emergent adverse events (AEs) and serious adverse events (SAEs) or adverse events of special interest (AESI) from baseline through Week 24, Week 52, Week 76 and Week 104
•	To evaluate the pharmacokinetic (PK) and	•	Serum guselkumab concentrations
	immunogenicity of guselkumab	•	Incidence of anti-guselkumab antibody
Ex	oloratory		
•	To evaluate the other efficacy of guselkumab in participants with SSc	•	Time to disease worsening: Increase from baseline ≥5 and ≥20% in mRSS OR decrease >10% from baseline in FVC %
		•	The proportion of participants who experience FVC decline compared with baseline at Week 24 and Week 52
		•	The proportion of participants who experience worsening of FVC at Week 24 and Week 52
		•	Change from baseline in fibrotic change assessed with high-resolution computed tomography (HRCT) at Week 24 and Week 52 in participants

CONFIDENTIAL – FOIA Exemptions Apply in U.S.

29

Objectives		Endpoints
		with baseline fibrosis/fibrotic changes
	•	The proportion of participants who experience worsening of fibrotic change assessed with HRCT at Week 24 and Week 52
	•	Change from baseline in Frequency Scale for the Symptoms of Gastroesophageal reflux disease (FSSG) score at Week 24 and Week 52
	•	Assessment of nailfold capillaries at Week 24 and Week 52

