	•	Change from baseline in Patient global assessment (PGA) at Week 24 and Week 52
	•	Change from baseline in Physician global assessment (PhGA) at Week 24 and Week 52
To evaluate the long-term efficacy of guselkumab in participant with SSc	•	Change from baseline and Week 52 in mRSS at Week 76 and Week 104
	•	The proportion of participants who experience worsening of mRSS at Week 76 and Week 104
	•	The proportion of participants achieving a score of 0.6 in American College of Rheumatology Combined Response Index in dcSSc (ACR CRISS) at Week 76 and Week 104
	•	Change from baseline in forced vital capacity (FVC) and percent predicted FVC at Week 76 and Week 104
	•	The proportion of participants who experience worsening of FVC at Week 76 and Week 104
	•	Change from baseline in the measured absolute diffusing capacity of the lung for carbon monoxide (DLCO) and the derived percent predicted DLCO at Week 76 and Week 104
	•	Change from baseline in Health Assessment Questionnaire-Disability Index (HAQ-DI) score at Week 76 and Week 104
	•	Change from baseline in digital ulcer counts at Week 76 and Week 104
	•	Change from baseline in fibrotic change assessed with high-resolution computed tomography (HRCT) at Week 76 and Week 104 in participants with baseline fibrosis/fibrotic changes
	•	The proportion of participants who experience worsening of fibrotic change assessed with HRCT at Week 76 and Week 104

Objectives	Endpoints
	• Change from baseline in Frequency Scale for the Symptoms of Gastroesophageal reflux disease (FSSG) score at Week 76 and Week 104
To evaluate the effect of guselkumab vs placebo on the pharmacodynamic (PD) and SSc disease biomarkers	• Change from baseline levels of skin (optional) and circulating (blood based) biomarkers over time to enable:
	Evaluation of target engagement in tissue/efficacy pharmacodynamic (PD) readouts
	• Single nucleotide polymorphisms (SNPs) frequency associated with IL-23 pathway

Refer to Section 8, STUDY ASSESSMENTS AND PROCEDURES for evaluations related to endpoints.

HYPOTHESIS

This is a PoC study aimed at detecting an early efficacy signal of guselkumab in participants with SSc, compared to placebo, to support further clinical development.

- The null hypothesis is that the treatment difference between guselkumab and placebo for the primary endpoint is 0.
- The alternative hypothesis is that the treatment difference between guselkumab and placebo for the primary endpoint is $\neq 0$.

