8.3.6. Adverse Events of Special Interest (AESI)

Any newly identified malignancy or case of active TB or ILD occurring after the first study intervention administration(s) in participants participating in this clinical study must be reported by the investigator to the sponsor or designee within 24 hours after being made aware of the event for SAEs. Investigators are also advised that active TB is considered a reportable disease in most countries. These events are to be considered serious only if they meet the definition of an SAE.

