5.5. Tertiary/Exploratory Efficacy Endpoints Analysis

The exploratory efficacy endpoints are listed as follows:

- Time to disease worsening: increase from baseline ≥ 5 and $\geq 20\%$ in mRSS or decrease $>10\%$ from baseline in FVC %
- The proportion of participants who experience FVC decline compared with baseline at Week 24 and Week 52
- The proportion of participants who experience worsening of FVC at Week 24 and Week 52
- Change from baseline in fibrotic change assessed with high-resolution computed tomography (HRCT) at Week 24 and Week 52 in participants with baseline fibrosis/fibrotic changes, including:

- 1) Change from baseline in quantitative lung fibrosis (QLF) score by whole lung and each lobe at Week 24 and Week 52 in participants with baseline QLF score of whole lung >0.
- 2) Change from baseline in quantitative interstitial lung disease (QILD) score by whole lung and each lobe at Week 24 and Week 52 in participants with baseline QILD score of whole lung >0.
- 3) Change from baseline in the absolute volume of consolidation, emphysema-like, ground glass, honeycombing, normal lung, reticulation texture pattern by whole lung and each lobe at Week 52.
- The proportion of participants who experience worsening of fibrotic change assessed with HRCT at Week 24 and Week 52, including:
 - 1) The proportion of participants who experience worsening of fibrotic change by whole lung and each lobe assessed with QLF of HRCT at Week 24 and Week 52, in participants with baseline QLF score of whole lung >0.
 - 2) The proportion of participants who experience worsening of fibrotic change by whole lung and each lobe assessed with QILD of HRCT at Week 24 and Week 52, in participants with baseline QILD score of whole lung >0.
- Change from baseline in frequency scale for the symptoms of gastroesophageal reflux disease (FSSG) score at Week 24 and Week 52
- Assessment of nailfold capillaries at Week 24 and Week 52, including:
 - 1) Change from baseline in average total number of capillaries/ length of nailfold; average total number of capillaries/ length of nailfold = sum (total number of capillaries of each finger) / sum (length of nailfold of each finger)
 - 2) Change from baseline in average number of enlarged capillaries (20-50 μ m)/ length of nailfold; average number of enlarged capillaries (20-50 μ m)/ length of nailfold = sum (Number of enlarged capillaries (20-50 μ m) of each finger) / sum (length of nailfold of each finger)

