 - 1) The proportion of participants who experience worsening of fibrotic change by whole lung and each lobe assessed with QLF of HRCT at Week 76 and Week 104, in participants with baseline QLF score of whole lung >0.
 - 2) The proportion of participants who experience worsening of fibrotic change by whole lung and each lobe assessed with QILD of HRCT at Week 76 and Week 104, in participants with baseline QILD score of whole lung >0.
- Change from baseline in Frequency Scale for the FSSG score at Week 76 and Week 104

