6.2. Appendix 2 Changes to Protocol-Planned Analyses

Not applicable.

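### SAP 5.5 limits the HRCT worsening proportion to participants with a baseline whole-lung score above 0, a limit the protocol does not set and the SAP does not declare

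*SAP*

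**What the plan says.** The protocol has two neighbouring exploratory HRCT endpoints, in the Synopsis (1.1) and in section 3.

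- The first carries a baseline condition: "Change from baseline in fibrotic change assessed with high-resolution computed tomography (HRCT) at Week 24 and Week 52 in participants with baseline fibrosis/fibrotic changes".
- The second carries none: "The proportion of participants who experience worsening of fibrotic change assessed with HRCT at Week 24 and Week 52".

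The long-term extension repeats the pattern. The change endpoint is limited to participants with fibrosis at baseline; the worsening endpoint is simply "The proportion of participants who experience worsening of fibrotic change assessed with HRCT at Week 76 and Week 104". SAP Table 1 (section 1.1) keeps the same contrast at all four visits.

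SAP 5.5 then makes the worsening proportion operational through two sub-items, by whole lung and by lobe:

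- the QLF item: "assessed with QLF of HRCT at Week 24 and Week 52, in participants with baseline QLF score of whole lung >0";
- the QILD item: "assessed with QILD of HRCT at Week 24 and Week 52, in participants with baseline QILD score of whole lung >0".

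The extension items carry the same conditions, for example "assessed with QLF of HRCT at Week 76 and Week 104, in participants with baseline QLF score of whole lung >0".

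SAP 5.5.1 defines worsening as a rise of at least 2% over the baseline score. It sets no baseline condition and does not say whether the 2% is absolute or relative. It also defines QILD as the sum of the fibrosis (QLF), ground-glass (QGG) and honeycomb (QHC) scores. SAP 5.5.2 bases exploratory efficacy analyses on the FAS. SAP Appendix 2, which records changes to protocol-planned analyses, reads "Not applicable".

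**The concern.** The conditions attached to the worsening proportion are the same ones SAP 5.5 uses for change from baseline. In the protocol and in SAP Table 1 such a condition belongs to the change endpoint alone, consistently across documents and visits. SAP 5.5 therefore narrows the population of a protocol endpoint, departs from the SAP's own Table 1, and leaves this out of the appendix meant for such departures.

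What is at stake is the question being answered. Fibrosis appearing where the baseline scan scored none is a clear form of worsening, and the protocol's wording includes it. Under the QLF item, the direct fibrosis measure, the proportion describes only participants who already had some scored fibrosis. A treatment effect on new fibrosis in the remaining participants would be partly or wholly invisible in this endpoint.

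**Working it through.** The plan gives no figure for this endpoint. The check is a comparison of the texts, followed by the SAP's rules applied to illustrative scores.

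**1. Where the baseline condition appears**

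| Source | Change from baseline | Worsening proportion |
|---|---|---|
| Protocol 1.1 and 3, Weeks 24 and 52 | limited | not limited |
| Protocol 1.1 and 3, Weeks 76 and 104 | limited | not limited |
| SAP Table 1, all four visits | limited | not limited |
| SAP 5.5, all four visits, QLF and QILD | limited (score >0) | limited (score >0) |
| SAP Appendix 2 | no change declared | no change declared |

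**2. Who can be counted**

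Rules from SAP 5.5 and 5.5.1:

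- QLF item: baseline whole-lung QLF >0, and QLF rises by at least the threshold.
- QILD item: baseline whole-lung QILD >0, and QILD rises by at least the threshold, where QILD = QLF + QGG + QHC.

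Take the threshold as 2 points. Assume new fibrosis adds 5 points to QLF and leaves the other components unchanged. The baseline scores are illustrative.

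| Baseline QLF, QGG, QHC | QLF item | QILD item | QLF rise ≥2 with no baseline limit |
|---|---|---|---|
| 0, 0, 0 | not in set | not in set | yes |
| 0, 5, 0 | not in set | counted (QILD 5 to 10) | yes |
| 0, 0, 3 | not in set | counted (QILD 3 to 8) | yes |
| 5, 0, 0 | counted (QLF 5 to 10) | counted (QILD 5 to 10) | yes |

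The first row is in neither item. The second and third are lost from the QLF item but can count under QILD. They count only if the sum rises: if 5 points of ground glass became 5 points of fibrosis, QILD would stay at 5 and nothing would be counted.

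The entry condition is on the whole lung, while worsening is also assessed by lobe. A lobe that starts at 0 can therefore count at lobe level when the whole-lung score is above 0.

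**3. How many participants**

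The documents do not give the share *s* with a baseline score of 0, so any value is an assumption.

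- Per arm of 28: 28 × 0.10 = 2.8 and 28 × 0.40 = 11.2, or about 3 to 11 left out.
- Whole trial, 56 × (1 − *s*):

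| Assumed *s* | 0 | 0.10 | 0.20 | 0.30 | 0.50 |
|---|---|---|---|---|---|
| Denominator | 56 | 50.4 | 44.8 | 39.2 | 28 |

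Because QILD contains QLF, the share left out of the QLF item is at least as large as the share left out of the QILD item.

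**4. The threshold at a baseline of 0**

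Read as relative, the rule is (visit − baseline) / baseline ≥ 0.02, which divides by zero when baseline is 0. Read as absolute, it is visit − baseline ≥ 2, which works at any baseline. The two also differ above 0: at a baseline of 5, a relative 2% is 5 × 0.02 = 0.1 points, against 2 points absolute.

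**The case against.** The strongest reply is that this is an exploratory endpoint in a proof-of-concept study. Protocol 9.4.4 leaves the detailed methods and data-handling rules for exploratory endpoints to the SAP, and extension endpoints are by default only described. The sub-items in SAP 5.5 follow the word including, so the list is not strictly closed, and SAP 5.6 promises listings. Clinically important new ILD is partly captured elsewhere: the first step of ACR CRISS uses HRCT to confirm ILD where none was seen before, alongside a confirmed FVC decline. If the 2% is relative, a baseline above 0 is needed for the rule to be computed at all, which may be why the condition is there.

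Much of this stands as a limit on importance. It does not remove the mismatch. Who belongs in the endpoint is more than a data-handling rule, no unrestricted analysis is specified anywhere, and Table 1 and Appendix 2 of the same SAP say otherwise.

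Three stronger readings are tempting, and the documents do not support them.

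- *New fibrosis is never counted.* It can count through QILD and through lobe-level assessment.
- *The omitted participant is in any case reported as an adverse event of special interest.* Protocol 8.3.6 covers newly identified ILD that the investigator reports, and SAP Appendix 8 defines the category by the investigator's assessment. Nothing says that a rise in a computed score triggers a report.
- *The no-ILD randomisation stratum shows that many participants score 0.* Protocol 8.2.5 allows ILD at screening to be judged from chest x-ray or HRCT and/or lung function tests. Nothing equates absence of ILD with a central QLF or QILD score of 0.

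**Conclusion.** The point holds as a mismatch between protocol and SAP with a definite but bounded consequence. At Weeks 24, 52, 76 and 104, a participant with whole-lung QLF of 0 at baseline cannot be counted as worsening in the QLF item, and a participant with whole-lung QILD of 0 is in neither item. The endpoint stated in the protocol is therefore not the one SAP 5.5 computes, and the difference is undeclared.

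The number affected is unknown. The range of 3 to 11 per arm rests wholly on an assumed zero-score share of 10% to 40%; if automated scoring gives almost everyone a score above 0, the loss is near nil. The mismatch itself is certain from the text; its practical effect is not.

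The condition is fixed at baseline, so it does not in itself bias the comparison between arms; it changes the question asked. The sample size, the significance level, and the primary and secondary conclusions are untouched.

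**What to change.** - **SAP 5.5:** report the worsening proportion, for QLF and QILD separately, in all FAS participants with a centrally readable baseline scan and a scan at the visit, including those with a baseline score of 0. Keep the set with baseline score >0 as a second row. Leave the condition on the change-from-baseline endpoint as it is.
- **SAP Appendix 2:** declare the restricted set as an addition to the protocol-planned analysis.
- **SAP 5.5.1:** state that the threshold is an absolute increase of 2 percentage points in score. This is a choice the SAP has not yet made, and it must be settled first, because a relative 2% is undefined at a baseline of 0.

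The cost is SAP wording only. Lung HRCT is already scheduled at screening and Weeks 24 and 52, and at Weeks 76 and 104 in the extension, without regard to ILD status. Scans of participants with a stent cannot be centrally read (Schedule of Activities footnotes), hence the readability condition. One small downside is that participants with clear lungs may dilute the overall rate, which the second row makes visible.

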5.5.1. Definition of Endpoints

Time to Disease Worsening

Time to disease worsening is calculated as the time from the date of randomization to the date of first occurrence of disease worsening, defined as: an increase from baseline ≥ 5 and $\geq 20\%$ in mRSS or decrease $>10\%$ from baseline in FVC %.

FVC Decline Compared with Baseline

FVC decline compared with baseline is defined as a decrease in postbaseline visits compared with baseline in FVC.

Worsening of FVC

Worsening of FVC is defined as an absolute change of % predicted FVC <-10.

High-resolution Computed Tomography (HRCT) Assessment

Lung involvement is one of the most important cause of morbidity and mortality in patients with SSc. Because of recent advancement of computer-based scoring, analysis of CT images is drawing attention as a method to assess fibrotic changes in ILD. Texture-based analysis and computer vision-based approaches can be applied to imaging data, and used to evaluate the extent of lung fibrosis in chest CT images. The main assessed parameters QLF, which included fibrotic reticulation patterns only; quantitative honeycomb (QHC); and quantitative ground glass (QGG). QILD scores represented the total ILD pattern and consisted of the sum of all three scores (ie, QLF+QGG+QHC). The score will be reported by central image reading.

Worsening of Fibrotic Change

Worsening of fibrotic change will be assessed by whole lung and each lobe with different parameters QLF and QILD separately, which is defined as increases of 2% or more compared to baseline score.

Symptoms of Gastroesophageal Reflux Disease (FSSG)

The FSSG is a succinct questionnaire to evaluate esophageal symptoms of gastroesophageal reflux disease (GERD) which is validated based on endoscopic esophagitis. The original version of FSSG consists of the most prevalent 7 acid-reflux related and 5 dysmotility-related symptoms of GERD with higher scores being more indicative of underlying GERD. Each score was determined as follows: 0 = never, 1 = occasionally, 2 = sometimes, 3 = often, and 4 = always. A negative change from baseline indicates improvement.

Nailfold Capillaroscopy

Nailfold capillaroscopy is a non-invasive method to visualize the nailfold capillaries and assess microvascular morphology. Nailfold capillary abnormalities are evaluated by using nailfold capillaroscopy. The typical changes of the nailfold capillaries during SSc include the total number of capillaries, capillary dimension, capillary morphology, hemorrhages, blood flow velocity in capillaries, and length of nailfold.

Patient Global Assessment (PGA)

Participant's overall health will be assessed using the patient-reported outcome instrument of PGA. The PGA would rate participant's overall health related to SSc in the past 7 days, using a 10 cm visual analogue scale where 0 = excellent and 10 = extremely poor. A negative change from baseline indicates improvement.

Physician Global Assessment (PhGA)

PhGA rated participant's overall health related to SSc in the past 7 days, using a 10 cm visual analogue scale where 0 = excellent and 10 = extremely poor. A negative change from baseline indicates improvement.

5.5.2. Analysis Methods

The analyses of exploratory efficacy endpoints will be based on the FAS.

Descriptive statistics, such as n, mean, SD, median, IQ range, minimum and maximum for continuous variables and counts and percentages for discrete variables will be used to summarize data when applicable. The analysis will be based on the observed data; therefore, no imputation of missing data will be performed.

All statistical testing will be performed between treatment groups at the 2-sided 0.2 significance level.

Continuous efficacy endpoints collected at multiple post baseline time points (ie, the endpoints of change from baseline) will be compared using a MMRM model. The model will include all available data through Week 24 (for endpoints at Week 24) or through Week 52 (for endpoints at Week 52).

The explanatory variables of the MMRM model will include treatment group, baseline value of the endpoint, stratification factors (presence of ILD, baseline mRSS and baseline anti-topoisomerase I antibody status), visit, treatment group by visit interaction, and baseline value of the endpoint by visit interaction as fixed effects. The estimates of the treatment difference between treatment groups will be provided by the difference in LSMs. The 80% CI for the differences in LSMs will be calculated based on the MMRM.

The analysis of change from baseline in fibrotic change assessed with HRCT at Week 24 and nailfold capillaries change at Week 24 will be performed using ANCOVA (analysis of covariance) model with baseline value of the endpoint as covariate, and stratification factors (presence of ILD, baseline mRSS and baseline anti-topoisomerase I antibody status) and treatment group as factors.

A logistic regression model will be used to compare the proportion of participants achieving selected endpoints (eg, worsening of % predicted FVC) between guselkumab and placebo. The analyses will include treatment group, stratification factors (presence of ILD, baseline mRSS and baseline anti-topoisomerase I antibody status) as factors. The same intercurrent events and composite strategy defined in Section 5.4.2.2 will be applied to following endpoints as well:

- The proportion of participants who experience FVC decline compared with baseline through Week 52
- The proportion of participants who experience worsening of FVC through Week 52

A summary of baseline values and change from baseline at Week 24 and Week 52 will be presented for nailfold capillaroscopy.

As to time to event endpoint, ie, time to disease worsening, it will be summarized by Kaplan-Meier method, with the median, 25th, and 75th percentiles and 95% CI for the quartiles. The comparison between guselkumab and placebo will use a Cox proportional hazards model adjusting for the stratification factors at randomization. An 80% CI for the hazard ratio (HR) will be produced. The

same intercurrent events and handling strategy defined in Section [5.4.2.2](#) will be applied to this endpoint as well, the detailed definition of censoring and event is described as below:

No.	Situation	Date of Event or Censoring	Outcome
1	Disease worsening: an increase from baseline ≥ 5 and $\geq 20\%$ in mRSS or decrease $>10\%$ from baseline in FVC %	First occurrence of disease worsening	Event
2	A prohibited change in SSc medication on or before Week 52	First occurrence of prohibited change	Event
3	Discontinuation of study intervention due to lack of efficacy or an AE of SSc before Week 52	Date of discontinuation of study intervention	Event
4	Initiation of rescue medication after Week 24 and through Week 52	Date of initiation of rescue medication	Event
5	Other	Date of last mRSS or FVC assessment through Week 52	Censored

Note: if participants had more than one items of 1,2,3,4 occurred, the date of first occurrence will be considered as event date.

Unless otherwise specified, LTE efficacy endpoints will only be summarized using descriptive statistics.

